6.10 Early Patient Termination / Patient Withdrawal

Patients who discontinue treatment early due to disease progression or withdrawal will be asked to have all end-of-treatment safety evaluations performed as described in the protocol (see *Table 1*).

7 ASSESSMENT OF SAFETY

7.1 Adverse Events

The PI is responsible for collecting and reporting adverse events (see Section 7.1.2). It is Sponsor responsibility to report relevant SAEs to the applicable regulatory authorities.

CONFIDENTIAL Page 37 of 61

Version: 1.0, Dated 12 September 2019

7.1.1 Definitions of adverse events

Any untoward medical occurrence in a patient or clinical investigation subject administered a pharmaceutical product and which does not necessarily have a causal relationship with this treatment. An adverse event (AE) can therefore be any unfavourable and unintended sign (including an abnormal laboratory finding), symptom, or disease temporally associated with the use of an investigational product, whether related or unrelated to the investigational product.

7.1.2 Recording of adverse events

All adverse events of any patient during the course of the trial will be reported in the case report form, and the investigator will give his or her opinion as to the relationship of the adverse event to trial drug treatment (i.e., whether the event is related or unrelated to trial drug administration). If the adverse event is serious, it should be reported immediately to Sponsor. Other untoward events occurring in the framework of a clinical trial are also to be recorded as AEs (i.e., AEs that occur prior to initiation of study drug that are related to a protocol-mandated intervention, including invasive procedures such as biopsies, medication washout, or no treatment run-in).

All AEs regardless of seriousness or relationship to Tenalisib, spanning from the informed consent drug until 30 calendar days after the last dose of study drug, discontinuation or completion of protocol-specific treatment as defined by the protocol for that patient, are to be recorded in the electronic Case Record Form (CRF).

7.1.3 Handling of adverse events

All adverse events resulting in discontinuation from the trial should be followed until resolution or stabilization. Patients must be followed for AEs for 30 calendar days after the last dose of study treatment. All new AEs occurring during this period must be reported and followed until resolution unless, in the opinion of the investigator, the adverse event or laboratory abnormality/ies are not likely to improve because of the underlying disease. In this case, the investigators must record his or her reasoning for this decision in the patient's medical record and as a comment on the CRF. After 30 days of completion of protocol-specific treatment or discontinuation, only AEs, SAEs, or deaths assessed by the investigator as treatment related are to be reported.

7.2 Adverse Event/Serious Adverse Event Causality Assessment

Causality is assessing the relationship of adverse event to the study drug. For this study, the causality assessment will be categorized as related and not related.

- **Related:** All toxicities should be considered related to Tenalisib unless there is a clear alternative explanation.
- **Not related:** If there is no temporal association, or another etiology has been identified as the cause, or the study drug cannot be implicated based upon the current information.

7.3 Serious Adverse Events

7.3.1 Definitions of serious adverse events

The definitions of serious adverse events (SAEs) are given below. The principal investigator is responsible for ensuring that all staff involved in the trial is familiar with the content of this section.

CONFIDENTIAL Page 38 of 61

An SAE or reaction is defined as any untoward medical occurrence that: results in death, is immediately life-threatening, requires at least a 24-hour in-patient hospitalization or prolongation of existing hospitalization, results in persistent or significant disability/incapacity, or is a congenital anomaly/birth defect.

The definition of SAE also includes any important medical event. Medical and scientific judgment should be exercised in deciding whether expedited reporting is appropriate in other situations, such as important medical events that may not be immediately life-threatening or result in death or hospitalization, but may jeopardize the patient or may require intervention to prevent one of the other outcomes listed in the previous definition. These should also usually be considered serious. Examples of such events are intensive treatment in an emergency room or at home for allergic bronchospasm; blood dyscrasias or convulsions that do not result in hospitalization; or development of drug dependency or drug abuse. *Progression of malignancy (including fatal outcomes)*, if documented by use of appropriate method (e.g. CT) or clinically confirmed, should not be reported as a serious adverse event.

Treatment within or admission to the following facilities is not considered to meet the criteria of "in-patient hospitalization" (although if any other SAE criteria are met, the event must still be treated as an SAE and immediately reported):

- Emergency Department or Emergency Room
- Outpatient or same-day surgery units
- Observation or short-stay unit
- Rehabilitation facility
- Hospice or skilled nursing facility
- Nursing homes, Custodial care or Respite care facility

Hospitalization during the trial for a pre-planned surgical or medical procedure (one which is planned prior to entry in the trial **or** planned in advance during the course of study; and not related to the study procedure/drug), does not require reporting as a serious adverse event to the Sponsor.

7.3.2 Serious adverse event reporting by Investigators

It is important to distinguish between "serious" and "severe" adverse events, as the terms are not synonymous. Severity is a measure of intensity; however, an AE of severe intensity need not necessarily be considered serious. For example, nausea which persists for several hours may be considered severe nausea but may not be considered an SAE. On the other hand, a stroke which results in only a limited degree of disability may be considered only a mild stroke but would be considered an SAE. Severity and seriousness should be independently assessed when recording AEs on the CRF and SAEs on the SAE Report Form.

Adverse events classified by the treating investigator as **serious** require expeditious handling and reporting to sponsor in order to comply with regulatory requirements. Serious adverse events may occur at any time from the signing of the informed consent form through the 30-day follow-up period after the last dose of drug. Sponsor/sponsor representative must be notified of all SAEs, regardless of causality, within 1 day of the first knowledge of the event by the investigator.

CONFIDENTIAL Page 39 of 61

Version: 1.0, Dated 12 September 2019

To report an SAE, the SAE report form should be completed with the necessary information. All SAEs occurring from the signing of consent until 30 calendar days of last dose of study drug must be reported to the Sponsor as SAEs on the SAE Report and followed until resolution (with autopsy report if applicable).

Deaths and other SAEs occurring >30 calendar days after last dose of study drug that are deemed 'possibly' or 'probably' related to Tenalisib must be reported as SAEs on the SAE Report within 1 day of first knowledge of the event by the treating physician or research personnel (with an autopsy report if available). Deaths occurring >30 calendar days after last dose of study drug and not attributed to study drug (e.g., disease progression) need not be reported as SAEs, but simply captured on the appropriate CRF.

The SAE report should be sent to the sponsor/sponsor representative via e-mail. The detailed SAE reporting process will be provided to the sites in the SAE reporting guidelines. Transmission of the SAE report should be confirmed by the site personnel submitting the report. Follow-up information for SAEs and information on non-serious AEs that become serious should also be reported to Sponsor as soon as it is available; these reports should be submitted using the SAE Report Form.

Investigators must report SAEs and follow-up information to their responsible IRB/IEC according to the policies of the responsible IRB/IEC.

7.3.3 Sponsor SAE reporting requirements

Sponsor/Sponsor representative is responsible for reporting relevant SAEs to the competent authority, other applicable regulatory authorities, and participating investigators, in accordance with ICH E6 guidelines, and local regulatory requirements.

Sponsor/sponsor representative is responsible for reporting unexpected fatal or life-threatening events associated with the use of the trial drugs to the regulatory agencies and competent authorities within 7 calendar days after being notified of the event.

The Sponsor will report all related, unexpected SAEs, including non-death/non-life-threatening related unexpected SAEs associated with the use of the trial medications to the local regulatory authorities (as applicable) by a written safety report within 15 calendar days of notification. Reporting to the IRB/IEC will be done according to institutional policy.

7.4 Severity of Adverse events

Severity of adverse events will be assessed according to National Cancer Institute (NCI)- CTCAE v5.0 with exceptions for platelet, hemoglobin and ANC that are recommended by iwCLL guidelines for the CLL (see below).

Grade*	Decrease in platelet† or Hb‡ (nadir) from baseline, %	Absolute neutrophil count (nadir)§ x 10 ⁹ /L	
0	No change to 10	≥2	
1	11-24	\geq 1.5 and \leq 2	
2	25-49	$\geq 1 \text{ and } < 1.5$	

CONFIDENTIAL Page 40 of 61

Version: 1.0, Dated 12 September 2019

3	50-74	≥0.5 and <1	
4	≥ 75	< 0.5	

^{*} Grades: 1-mild; 2-moderate; 3-severe; 4-life-threatening; 5-fatal. Death occurring as a result of toxicity at any level of decrease from baseline will be recorded as grade 5.

§ If the absolute neutrophil count (ANC) reaches $<1\times10^9/L$, it should be judged to be grade 3 toxicity. Other decreases in the white blood cell count or in circulating granulocytes are not to be considered because a decrease in the white blood cell count is a desired therapeutic end point. A gradual decrease in granulocytes is not a reliable index in CLL for stepwise grading of toxicity. If the ANC is $<1\times10^9/L$ before therapy, the patient is not evaluable for toxicity referable to the ANC. The use of G-CSF is irrelevant for the grading of toxicity but should be documented.

7.5 Recording of Adverse Events and Serious Adverse Events

Investigators should use correct medical terminology/concepts when recording AEs or SAEs on the SAE Report Forms and AE CRF. Avoid colloquialisms and abbreviations. All AEs, including those that meet SAE reporting criteria, should be recorded on the AE CRF; AEs that meet the definition of an SAE should additionally be reported following the procedures noted in above sections.

7.5.1 Diagnosis vs. signs and symptoms

All AEs should be recorded individually in the patient's own words (verbatim) unless, in the opinion of the Coordinating Investigator or designated physician, the AEs constitute components of a recognized condition, disease, or syndrome. In the latter case, the condition, disease, or syndrome should be named rather than each individual sign or symptom. If a constellation of signs and/or symptoms cannot be medically characterized as a single diagnosis or syndrome at the time of reporting, each individual event should be recorded as an AE or SAE as appropriate on the relevant form(s) (SAE Report Form and/or AE CRF). If a diagnosis is subsequently established, it should be reported as follow-up information. If a diagnosis is determined subsequent to the reporting of the constellation of symptoms, the signs/symptoms should be updated to reflect the diagnosis.

7.5.2 Persistent or recurrent adverse events

A persistent AE is one that extends continuously, without resolution, between patient evaluation time points. Such events should only be recorded once on the SAE Report Form. If a persistent AE becomes more severe or lessens in severity, AE should be recorded separately with onset date as date of change of severity in CRF.

A recurrent AE is one that occurs and resolves between patient evaluation time points, and subsequently recurs. All recurrent events should be recorded separately on an SAE Report Form and/or CRF.

CONFIDENTIAL Page 41 of 61

[†] Platelet counts must be below normal levels for grades 1-4. If, at any level of decrease the platelet count is $<20 \times 10^9/L$, this will be considered grade 4 toxicity unless a severe or life-threatening decrease in the initial platelet count (e.g., $20 \times 10^9/L$) is present at baseline, in which case the patient is not evaluable for toxicity referable to platelet counts.

[‡] Hb levels must be below normal levels for grades 1-4. Baseline and subsequent Hb determinations must be performed as per the schedule of events. The use of erythropoietin is irrelevant for the grading of toxicity but should be documented.

Version: 1.0, Dated 12 September 2019

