6 TRIAL ASSESSMENT AND PROCEDURE

6.1 Overview

Schedule of Event summarizes the trial procedures to be performed at each visit and is divided into following.

- 1. Screening (Day -28 day to Day 0)
- 2. On treatment procedures (C1D1 to C8D1)
- 3. End of Treatment (Day +7 from last dose)
- 4. End of Study (Day +30 from last dose)

Individual trial procedures are described in detail below. It may be necessary to perform these procedures at unscheduled time points if deemed clinically necessary by the investigator.

Furthermore, additional evaluations/testing may be deemed necessary by the investigator and or the sponsor for reasons related to subject safety. In some cases, such evaluation/testing may be potentially sensitive in nature (e.g., HIV, HBV, HCV and CMV), and thus local regulations may require that additional informed consent be obtained from the subject. In these cases, such evaluations/testing will be performed in accordance with local regulations.

Protocol No. RP6530-1901 Rhizen Pharmaceuticals SA

Version: 1.0, Dated 12 September 2019

Table 1: Study Assessments and Treatment Schedule												
Day	Screening	C	C1	C	22	C3	C4	C5	C6	C7	C8/ EOT ¹⁸	EOS ¹⁹
Day		D 1	D15	D 1	D15	D 1	D1	D1	D1	D1	D1	-
Window period	-28	0	±1	±1	±1	±3	±3	±3	±3	±3	+7	+30
Study Days	D-28 to 0	1	15	29	43	57	85	113	141	169	197	227
Informed consent ¹	X	-	-	-	-	-	_	-	-	-	-	-
Demographics ²	X	-	-	-	-	-	-	-	-	-	-	-
Medical history ³	X	-	-	-	-	-	-	-	-	-	-	
Vitals ⁴	X	X	X	X	X	X	X	X	X	X	X	-
Height and weight ⁵	X	X	X	X	X	X	X	X	X	X	X	-
Complete physical exam ⁶	X	-	-	-	-	-	-	-	-	-	X	-
Abbreviated physical exam ⁶	-	X	X	X	X	X	X	X	X	X	-	-
ECOG Performance Status	X	X	_	-	_	X	_	X	_	_	X	-
Rai Staging	X	-	-	ı	-	ı	-	-	-	-	-	-
Laboratory assessment												
Complete blood count ⁷	X	X	X	X	X	X	X	X	X	X	X	-
Chemistry panel I ⁸	X	X	X	X	X	X	X	X	X	X	X	-
Chemistry panel II ⁹	X	X	-	-	-	X	-	X	-	-	X	-
Serology ¹⁰	X	-	-	-	-	-	-	_	-	-	-	
PT and INR ¹¹	X	X	X	X	X	X	X	X	X	X	X	_
Urinalysis (routine)	X	X	X	X	X	X	X	X	X	X	X	-
Pregnancy test ¹²	X	X	-	ı	-	ı	-	-	-	-	-	-
12-lead ECGs ¹³	X	X	-	X	-	X	-	X	-	-	X	-
Bone marrow biopsy/ aspirate ¹⁴	X	-	-	-	-	-	_	-	-	-	-	-

CONFIDENTIAL Page 29 of 61

Protocol No. RP6530-1901 Rhizen Pharmaceuticals SA

Version: 1.0, Dated 12 September 2019

Disease assessment												
Radiological scan/imaging ¹⁵	X	-	1	1	-	X	1	X	ı	1	X	-
Treatment administration												
Tenalisib treatment ¹⁶	-	X	X	X	X	X	X	X	X	X	X	-
Tenalisib dispensing	-	X	-	X	-	X	X	X	X	X	X	-

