- 11. PT and INR. In case of abnormality, additional tests including aPTT to be done as per investigator discretion. This test will be performed at supplementary visits if clinically indicated.
- 12. Pregnancy test is required for women of childbearing potential. A serum pregnancy test will be performed at screening; and serum/urine pregnancy test at C1D1 (within 72 hours) of dosing. Urine pregnancy test will be performed at other visits as indicated.
- 13. 12-lead ECG: ECG will be done at Pre-dose on scheduled timepoints on the day of drug administration. Additional ECGs will be obtained if clinically indicated. Triplicate ECGs will be performed to confirm the significant changes of single ECG.
- 14. A bone marrow biopsy/aspirate: Unilateral bone marrow aspiration and/or biopsy will be performed at investigator discretion in patients for whom assessment of extent of CLL involvement and bone marrow cellularity is important in determining eligibility. However, post initiation of treatment, bone marrow biopsy should be done to confirm potential CR.
- 15. Radiological assessment: "Diagnostic quality" CT scan of neck/chest/abdomen/pelvis, as applicable, will be done at the time of screening within 28 days of C1D1. The scan and other investigations to document measurable or evaluable disease should be performed ≤28 days prior to initiation of treatment or as approved by the medical monitor if it is out of 28-days window period. Following screening, CT scans should be repeated at C3D1 (± 7 days), C5D1 (± 7 days) and C8D1 (± 7 days) or at end of the treatment (EOT) visit.
- 16. Tenalisib will be administered orally twice a day in 28-days of cycle for 7 cycles (C1D1 to C8D1) in absence of disease progression or toxicity warranting discontinuation of therapy.
- 17. All AEs regardless of seriousness or relationship to study drug should be recorded spanning from the informed consent drug until 30 calendar days after the last dose of study drug.
- 18. Post C8D1, patient experiencing clinical benefit with no evident disease progression will be given the opportunity to enroll in an open-label compassionate medication use study and will be followed up. Excluding patients who participate in compassionate medication use study [Protocol:RP6530-1803], all other patients will undergo the end-of-treatment (EOT) assessments within 7 days after the last dose of study drug or discontinuation from the study.

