10.6.2 Adverse Events

Analysis set: Safety

Note: If needed, adverse event data may be presented for all screened patients.

The frequency of adverse events (AEs) will be computed by counting each patient only once per MedDRA [Version 23.0 (Hierarchy) or higher] preferred term and according to the maximum NCI CTCAE v.5.0 grade attained by the patient over the specified period. The percentage of

patients with an event will be calculated using the number of patients in the safety analysis set as the denominator.

Standard Summaries of Adverse Events

Treatment Emergent Adverse Events (TEAEs) are those that start on or after the date of first dose of study medication.

An overall summary of TEAEs (number and percentage of patients along with the number of events) will be presented with the following:

- Any non-TEAE
- Any TEAE
- Treatment Related TEAEs
- Serious non-TEAEs
- Serious TEAEs
- Treatment Related Serious TEAEs
- Grade 3 or 4 TEAEs
- Treatment Related Grade 3 or 4 TEAEs
- TEAEs leading to discontinuation
- Treatment Related TEAEs leading to discontinuation
- Serious TEAEs leading to discontinuation
- Treatment Related Serious TEAEs leading to discontinuation
- TEAEs leading to dose interruptions/dose reductions
- Fatal TEAEs
- Treatment Related Fatal TEAEs
- Protocol-Defined Adverse Events of Special Interest:
 - Pregnancy, abortion, birth defects/congenital anomalies
 - Overdose

Summaries showing the number of patients (n, %) along with number of events by SOC and PT will be provided for the following:

- TEAEs (Related/ Not Related/ Total)
- Grade 3, 4 and 5 TEAEs (Related/ Not Related/ Total)
- Treatment-Emergent SAEs (Related/ Not Related/ Total)
- TEAE with maximum CTCAE grade
- Treatment-Related TEAEs with maximum CTCAE grade
- Deaths

The adverse events data will also be listed for individual patients.

- Any non-TEAE
- AEs
- Related TEAEs
- Treatment Emergent Grade 3, 4 and 5 AEs
- Treatment Related Grade 3, 4 and 5 AEs
- SAEs

- Treatment Related SAEs
- TEAE leading to discontinuation

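### A persistent AE gets a new onset date at every grade change while TEAEs are defined by start date alone, so a pre-dose AE that only improves becomes a TEAE and one on-treatment episode can count as several events

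*Protocol*

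**What the plan says.** Protocol 7.5.2 defines a persistent AE as one that continues without resolving between evaluations. If such an AE "becomes more severe or lessens in severity, AE should be recorded separately with onset date as date of change of severity in CRF". The instruction covers improvement as well as worsening. The same section says of persistent events: "Such events should only be recorded once on the SAE Report Form". That limit names the SAE form and not the AE CRF. A recurrent AE, which resolves and comes back, is recorded separately each time.

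AEs are collected before dosing. Protocol 7.1.2 sets the window as "spanning from the informed consent drug until 30 calendar days after the last dose of study drug", and Protocol 6.2.1 allows consent up to 30 days before treatment starts. The SAP expects such records, because its overall AE summary has rows for non-TEAEs and serious non-TEAEs.

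SAP 10.6.2 then states: "Treatment Emergent Adverse Events (TEAEs) are those that start on or after the date of first dose of study medication". It also states: "An overall summary of TEAEs (number and percentage of patients along with the number of events) will be presented". The tables by system organ class and preferred term report event numbers as well. For patient counts, the SAP counts a patient once per preferred term, at the highest grade reached. It does not define one event, does not say how records split by grade are linked, and sets no condition that a pre-dose AE must have worsened.

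**The concern.** Splitting records by grade is a reasonable way to collect data. The difficulty arises when a start-date definition is applied to the split records, because the start date of a later record is the date the grade moved, not the date the event began. A downgrade after first dose therefore looks like a new event on treatment.

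Safety and tolerability is a secondary objective, and the AE tables are its main output. In a study of 21 patients, one misclassified patient visibly changes a percentage. The event columns would partly measure how often a grade changed, and how often it was checked, instead of how many episodes occurred.

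**Working it through.** The documents state no figure that depends on this point and give no AE data. The check applies the written rules to assumed AE histories and compares the result with a linked-episode rule.

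**Inputs**
- New CRF record and onset date at each grade change, up or down (Protocol 7.5.2).
- AEs recorded from consent (Protocol 7.1.2; Table 1, footnote 17).
- TEAE if the record starts on or after first dose; event numbers reported (SAP 10.6.2).
- One count per patient per preferred term, at maximum grade (SAP 10.6.2).
- 21 patients enrolled (SAP 6). The number dosed is not stated.

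**Rules compared**
- *As written:* each record with onset on or after first dose is one TEAE event. An on-treatment episode with k grade changes gives k + 1 events. An episode that began before dosing gives one TEAE event for each grade change after first dose.
- *Linked:* one event per continuous episode. It is treatment-emergent only if it began on or after first dose, or if its grade after first dose exceeds the last pre-dose grade.

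| Assumed history | TEAE events, as written | TEAE events, linked | Patients with a TEAE, as written / linked |
|---|---|---|---|
| A. Starts in screening at Grade 2, falls to 1 after dosing | 1 | 0 | 1 / 0 |
| B. Starts in screening at Grade 3, falls to 2, then 1 after dosing | 2 | 0 | 1 / 0 |
| C. On treatment, grades 1-2-3-2-1 (k = 4) | 4 + 1 = 5 | 1 | 1 / 1 |
| D. On treatment, grades 3-4-3 (k = 2) | 2 + 1 = 3, all Grade 3/4 | 1 (Grade 4) | 1 / 1 |

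**Reading the table**
- In A and B both the patient count and the event count are wrong. Counting once per preferred term does not help, because the downgrade record itself meets the TEAE definition. SAP 9.3.1 does not help either: it imputes missing or partial dates, and this date is complete.
- In C and D only the event count changes. The patient is counted once, at maximum grade 3 in C and 4 in D, under either rule.

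**Size of the patient-level effect**
- Each patient like A or B, with no other TEAE in that preferred term, adds 1/21 = 4.8 percentage points to the term. Two such patients add 2/21 = 9.5, and three add 3/21 = 14.3.
- These figures assume that all 21 were dosed. With 20 in the safety set, one patient is 1/20 = 5.0 points; with 19, it is 1/19 = 5.3.

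**The case against.** The strongest reply is that the reach is small, and most of it stands.

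- **Patient-level tables are largely protected.** Because of the once-per-term, maximum-grade rule, splitting an on-treatment episode cannot inflate the patient count for a term or change its maximum grade. This stands and confines the second effect to the event columns.
- **The false-TEAE route is narrow.** Conditions present at the start of the trial go to medical history and become AEs only if they worsen (Protocol 7.5.6). Exclusion criterion 16 also removes most unresolved prior-therapy toxicity of Grade 2 or above. What is left is AEs that start between consent and first dose, are still present at dosing, and then step down without resolving. The number of these is unknown. This stands, but the group is not empty by design: Protocol 7.1.2 expressly calls for recording pre-dose events, including those caused by procedures such as biopsies.
- **Splitting has a benefit.** It lets a start-date definition pick up pre-dose AEs that worsen on drug. This is true. Only downgrades go wrong, and the error overstates toxicity.
- **The analysis is descriptive, and records can be traced.** No inferential safety analysis is planned, the study closed in Stage 1, and AEs are listed by patient. This limits the consequence but does not make the tables correct.

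Two stronger readings might be inferred. One is that splitting dilutes the share of events that are Grade 3/4. The SAP plans no such share: it reports patients (number and percentage of the safety set) and a count of events. In history C the Grade 3/4 row shows 1 patient and 1 event under either rule. The other is that CRF and SAE-form counts will conflict. Protocol 7.5 has SAEs entered on both forms, and nothing in the documents plans a comparison of event counts between them.

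**Conclusion.** The point holds within limits. Following the written rules, an AE that starts between consent and first dose and only improves after dosing becomes a TEAE, at both patient and event level. That is a wrong classification produced by stated rules, and not just missing detail. Separately, one continuous on-treatment episode with k grade changes is reported as k + 1 events.

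The first effect is worth 4.8 percentage points per affected patient and preferred term, if all 21 enrolled patients were dosed and the patient has no other TEAE with that term. The second changes event counts only. The grade paths are illustrative, and the actual size cannot be computed from the documents. They do not support a claim that patient-level TEAE rates are inflated in general.

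**What to change.** Add a derivation step to SAP 10.6.2:

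1. Link records of the same preferred term in a patient only where one ends and the next starts at a change of severity without resolution. Keep recurrent AEs separate, as Protocol 7.5.2 requires.
2. A linked episode that began before first dose is treatment-emergent only if its grade after first dose exceeds the last pre-dose grade. An episode that began on or after first dose is treatment-emergent as now.
3. Count events as linked episodes. Each takes its maximum grade from first dose onward, and is related or serious if any of its records from first dose onward is. State a similar rule for the rows on discontinuation and dose change.
4. Keep the grade-level records in the listings.

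This needs no protocol amendment and no change to data collection, provided each CRF record carries start date, end date and grade. The eCRF is not among the documents, so this should be confirmed. The cost is a little more programming, and manual review of links where dates are partial or imputed under SAP 9.3.1, since imputed dates can create false gaps or overlaps.
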